9.3 Criteria for Home Blood Pressure

For each test item, home blood pressure will be determined according to the table below for evaluable data (i.e., non-missing data) obtained within 3 days after the last study drug administration for the Treatment Period (including Day 3 after the last study drug administration for the Treatment Period; the day after the last study drug administration for the Treatment Period to be defined as Day 1). The value before calculating the representative value on each measuring day (value described in the case report form) will be used for this determination.

Table 9.d Criteria for Home Blood Pressure

Tost Itam	Test Item Gender Age (years)		Criteria	
Test Item			Lower	Upper
Home sitting systolic blood pressur (mmHg)	e _	-	-	≥ 99th percentile of Table 5.a + 15 mmHg
Home sitting diastolic blood pressur (mmHg)	e _	-	-	≥ 99th percentile of Table 5.a + 10 mmHg

Classifying Subjects for the Overall Treatment Period

For each test item and subject, home blood pressure will be determined according to the conditions [1] to [3] provided below.

- [1] A subject will be classified as those "with markedly abnormal blood pressure" if he/she has at least one data that "meets the Criteria for Home Blood Pressure" among the evaluable data obtained after the study drug administration for the Treatment Period.
- [2] A subject will be classified as those "without markedly abnormal blood pressure" if he/she does not meet condition [1] and has at least one data that does "not meet the Criteria for Home Blood Pressure" among the evaluable data obtained after the study drug administration for the Treatment Period.
- [3] A subject who does not meet conditions [1] or [2] will be excluded from the analysis of home blood pressure for that item.

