7.2 Exclusion Criteria

Any subject who meets any of the following criteria will not qualify for entry into the study:

1. The subject has received any investigational compound within 30 days prior to screening or is participating in another clinical study or a post-marketing clinical study.
Note: This does not apply to subjects participating in observational studies without interventional or invasive therapy.
2. The subject previously received therapy with azilsartan.
Note: This does not apply to subjects participating in single dose pharmacokinetic studies of TAK-536.

3. The subject has poorly controlled hypertension indicated by an office sitting systolic blood pressure higher by at least 15 mmHg and/or an office sitting diastolic blood pressure higher by at least 10 mmHg than the 99 percentiles of the reference blood pressure values of children by gender and age (Table 5.a).
4. The subject has a diagnosis of malignant or accelerated hypertension.
5. The subject was noncompliant (< 70% or > 130%)* with the study drug during the Run-in Period.
*: The proportion of the number of the received the study drug to the number of the study drug which the subjects should receive.
6. The subject has severe renal dysfunction (eGFR < 30 mL/min/1.73 m²), is receiving dialysis, has a renovascular disease affecting one or both kidneys, severe nephrotic syndrome not in remission, or a serum albumin level < 2.5 g/dL.
7. The subject has a history of, or the signs/symptoms of serious cardiovascular, hepatobiliary, gastrointestinal, endocrine (eg, hyperthyroidism, Cushing's syndrome), hematological, immunological, urinogenital, psychiatric disease, cancer, or any other disease that adversely affects subject's health, or, in the opinion of the investigator or subinvestigator, potentially confounds the study results.
8. The subject has hemodynamically significant left ventricular outflow obstruction due to aortic stenosis or aortic valvular disease, or is scheduled to undergo a medical procedure affecting blood pressure during the study (eg, correction of arterial anomaly).
9. The subject has a history of or concurrent clinically significant abnormality of 12-lead ECG that, in the opinion of the investigator or subinvestigator, disqualifies the subject for participation in the study.
10. The subject has poorly controlled diabetes mellitus indicated by HbA1c > 9.0% at screening.

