Sitting blood pressure will be repeatedly measured 3 times at 1 to 2 minute intervals after the subject has been sitting at rest for at least 5 minutes and recorded in the subject source documents and eCRF. However, if 2 of the 3 systolic blood pressure measurements differ by more than 8 mmHg or diastolic blood pressure measurements differ by more than 5 mmHg, a second set of 3 sitting blood pressure measurements should be obtained and only the second set of readings should be recorded in the eCRF (even if these still differ by > 8 mmHg for systolic blood pressure or 5 mmHg for diastolic blood pressure). Original and repeat readings must all be recorded in the source documents with an explanation.

The arithmetic mean (rounded to integers) of 3 measurements of a session will be used for determination of the subject eligibility.

The pulse rate measured at the last measurement of the sitting blood pressure will be used as the sitting pulse rate value.

Sitting blood pressure must be measured after resting in a sitting position for at least 5 minutes. An appropriately sized cuff (40% of the arm's perimeter) should be used, and applied to an upper arm held at the heart level. All measurements must be made on the same arm using the same-sized cuff. Every effort should be made to standardize the condition of office blood pressure measurements as possible, such as measurement time, the same blood pressure device should be used, whenever possible, by the same investigator, subinvestigator, or the study collaborator.

<Measuring standing blood pressure and standing pulse rate>

Standing blood pressure will be measured to evaluate the orthostatic vital signs at the scheduled visit of Week 0, 12, 24 and 52. After measuring the sitting blood pressure, standing blood pressure will be measured once after the subject has been standing for 2 minutes. Standing systolic and diastolic blood pressure will be also measured with the same device which measures sitting blood pressure on the same arm. For standing blood pressure measurements, the arm should be supported and extended such that the cuff is at heart level. Standing pulse rate will be measured once during the subject maintains a standing position.

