9.1.6 Measuring Home Blood Pressure

Each subject, the subject's parent, or the subject's legal guardian will be provided a home blood pressure meter and adequately informed of the measurement procedures at the start of the Run-in Period (Week -2) by the sponsor through the study site.

The subject, the subject's parent, or the subject's legal guardian will be instructed to measure home blood pressure (systolic and diastolic), preferably consecutive 2 times daily immediately before the study drug administration for 1 week each before and after the visit at the start of the Treatment Period I, and for 1 week after the following day of a visit of each time point between Week 2 and Week 8 of the Treatment Period I (including visit at Week 6, when performed), and for 1 week from the day before the visit at Week 12 of the Treatment Period I.

The subject should measure blood pressure 2 times in a row after having been sitting for at least 5 minutes with the blood pressure cuff applied to the same arm as used to measure blood pressure at the visits. The blood pressure measurements should be recorded in patient diary and reviewed by the investigator or subinvestigator at each visit. The blood pressure measured twice immediately before the study drug administration should be recorded in CRFs. The subject, the subject's parent, or the subject's legal guardian will be instructed to inform the study site if a home sitting systolic blood pressure which is higher by at least 15 mmHg and/or a home sitting diastolic blood pressure which is higher by at least 10 mmHg than the 99 percentiles of the reference blood pressure values of children by gender and age in Table 5.a. The subject, the subject's parent, or the subject's legal guardian will be instructed by the investigators to visit the study site to measure blood pressure again if needed. If the elevated blood pressure is confirmed by repeat measurements at the study site, the subject is to be considered to discontinue the study.

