For home blood pressure, the mean of 2 values on a given measuring day will be used as the representative value of that measuring day (do not round off). If only one measurement is performed on a given measuring day, that value will be used as the representative value. Next, based on Table 7.h, the mean of the representative values on each measuring day within each acceptable time window (rounded to integers) will be used as the values for each visit. However, if the representative values on the measuring day within the time window include values for 3 days or less, this visit will be handled as missing. At the End of Treatment Period I, among the values from Week 0 (postdose) to Week 12 included based on Table 7.h, the value at the last visit excluding missing data will be used. If the acceptable time window overlaps at different visits, the value will be included in the earlier visit and excluded from the later visit.

Table 7.h Visit Window of Home Blood Pressure

		Acceptable Tim	Acceptable Time Window	
Visit	Reference Day	Number of Days from Reference Day*	Follow-up Day	
Week 0 (predose)	Visit day for Week 0	−7 to −1		
Week 0 (postdose)	Visit day for Week 0	2 to 8	< 4	
Week 2	Visit day for Week 2	2 to 8	< 4	
Week 4	Visit day for Week 4	2 to 8	< 4	
Week 8	Visit day for Week 8	2 to 8	< 4	
Week 12	Visit day for Week 12	−7 to −1	< 4	

^{*:} The day before the Reference Day will be defined as Day -1 and the Reference Day as Day 1.

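### SAP 9.3 classes a child as markedly abnormal on any one raw home reading, so the count depends on reading noise and number of readings and has no predose reference

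*SAP*

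**What the plan says.** SAP 9.3 with Table 9.d sets the systolic limit at "≥ 99th percentile of Table 5.a + 15 mmHg" and the diastolic limit at the 99th percentile plus 10 mmHg. The data used are individual readings, not averages: "The value before calculating the representative value on each measuring day (value described in the case report form) will be used for this determination". One exceedance is enough. For each of systolic and diastolic pressure, a child is classed as *with markedly abnormal blood pressure* if there is "at least one data that 'meets the Criteria for Home Blood Pressure' among the evaluable data obtained after the study drug administration". No second reading, second day or site repeat is asked for. The result is display (3) in SAP 7.11.3.

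Protocol 9.1.6 asks for preferably two readings in a row each day, both entered in the CRF. The home weeks fall before and after Week 0, after Weeks 2, 4 and 8 (and Week 6 if that visit is held), and around Week 12. Protocol 7.4 item 5 and 9.1.6 use the same limits as a home alert that the family reports to the site.

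For all other home pressure tables, SAP 7.1.3 averages the two readings of a day and then the days of the window, and a visit with no more than 3 such days gets no value.

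**The concern.** With one exceedance enough, the table in effect reports each child's highest reading. The chance of being counted then rises with the scatter of single readings and with the number recorded. That number differs between children for reasons unrelated to safety. Two readings a day are only preferred, so adherence matters. A Week 6 visit is held when further lowering of pressure is needed, so those children get an extra home week. Table 7.h has no Week 6 window, so these extra readings enter no visit average, yet SAP 9.3 as worded still counts them.

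There is also nothing to compare the count with. The study has one arm, and the placebo run-in week is collected but not classified. A reader who sees some number of children with markedly abnormal pressure on TAK-536 cannot tell how many would have been counted in a home week before treatment.

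**Working it through.** **Plan's own figure.** SAP 9.3 states no reading count or error rate. The plan's only computed figure, at least 90% power with 50 children, does hold (0.990 diastolic, 0.989 systolic, noncentral t), but it is not an input here.

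**Readings (Protocol 9.1.6, full adherence).** After first dose: 5 weeks × 7 days × 2 = 70. With Week 6: 6 × 7 × 2 = 84, which is 20% more. Week 0 (predose): 1 × 7 × 2 = 14.

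**Distance to the limit (Table 5.a, ages 6 to 15, both sexes).** Systolic (99th + 15) − 95th is 22 or 23 mmHg; for a boy of 10, 127 + 15 − 119 = 23. Diastolic (99th + 10) − 95th is 17 or 18 mmHg. Take 22.5 for systolic pressure. A child whose usual home value is 5 mmHg above the 95th percentile is then 17.5 mmHg below the limit.

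**SD of one home reading.** Not in the documents; assumed 6, 8 and 11 mmHg. The top value is the planning SD of office systolic change divided by √2 (15.5/1.414 = 11.0). It includes differences in response between children, so it is not an estimate of reading noise.

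**Independent readings, no change over time.** p = 1 − Φ(17.5/SD); P(flag) = 1 − (1 − p)^m.

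| SD | p | m = 14 | m = 35 | m = 70 | m = 84 |
|---|---|---|---|---|---|
| 6 | 0.18% | 2.4% | 6.0% | 12% | 14% |
| 8 | 1.4% | 18% | 40% | 64% | 70% |
| 11 | 5.6% | 55% | 87% | 98% | 99% |

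**Allowing for paired readings.** Assume 70% of the variance is shared by the two readings of a day, and simulate 40,000 children with 35 days × 2 readings. P(flag) is about 11%, 58% and 96%. For a child exactly at the 95th percentile it is 0.6%, 14% and 71%.

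**With a treatment fall.** Let systolic pressure fall in equal steps of 1.9 mmHg per home week, from 1.9 in the first to 9.5 in the fifth, 9.5 being the plan's assumed office change. P(flag) becomes about 1%, 17% and 70%. The path matters: a straight line from zero at first dose to 9.5 mmHg at Week 12 gives about 3%, 26% and 80%.

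**Confirmed rule: daily value at the limit on at least 2 days of one home week, no fall.**
- Variance of the daily mean = SD² × (0.7 + 0.3/2) = 0.85 SD², so q = 1 − Φ(17.5/(0.922 SD)) = 0.08%, 0.88%, 4.2%.
- One week: 1 − (1 − q)^7 − 7q(1 − q)^6 = under 0.01%, 0.16%, 3.2%.
- Five weeks: 1 − (1 − weekly value)^5 = about 0%, 0.8%, 15%.

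**Why the reference must be by week.** In the table above, the same unchanged child is flagged in 2.4%, 18% and 55% of cases on 14 predose readings, but in 12%, 64% and 98% on 70 later ones. Comparing the predose week with the whole period would show a rise where none exists.

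**The case against.** *The limit is the protocol's own.* Protocol 7.4 item 5 and 9.1.6 ask the family to report a home value at this limit, with no repeat first, so the row tabulates the alert. This stands, and it is the reason to keep the row. A reader might infer that the protocol acts on a home reading only after confirmation. It does not say that: the condition "If the elevated blood pressure is confirmed by repeat measurements at the study site" precedes only the step of considering discontinuation. A reader might also take exclusion criterion 3 as the source of the limit, since the numbers agree. That criterion concerns office pressure, and "The arithmetic mean (rounded to integers) of 3 measurements of a session will be used for determination of the subject eligibility".

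*Any-occurrence counts are ordinary.* SAP 9.2 classifies laboratory values in the same way. This stands in part, but SAP 7.11.2.1 lists 8 laboratory visits after first dose, against up to 70 or 84 home readings.

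*Averages are reported elsewhere.* SAP 7.11.3 gives visit means, changes from Week 0 (predose) and case plots, and SAP 7.8.3 adds confidence intervals. The minimum-days rule in SAP 7.1.3 governs when a visit mean is usable and does not contradict a screen on raw values. This stands: the count is one descriptive display, and no test or decision rests on it.

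*The size is assumed.* This stands too. A reader might infer that most flags will be noise, or that steady children will often be flagged. Without a home-reading SD, neither follows: at an SD of 6 mmHg with a gradual fall, the chance is about 1%.

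**Conclusion.** On the text, the classification rests on a single unconfirmed reading out of up to 70 (84 with Week 6), opportunity differs between children, and no predose count is planned. The count therefore mixes blood pressure level with reading noise and number of readings. The direction is certain. The size is not: for a child 5 mmHg above the systolic 95th percentile it runs from about 11% to 96% with no change in pressure, and from about 1% to 70% with a stepwise fall of 9.5 mmHg, over assumed SDs of 6 to 11 mmHg and an assumed 70% shared within-day variance. The Week 6 effect is modest: at an SD of 8 mmHg the independent-reading figure goes from 64% to 70%. The documents do not support the stronger statement that the count is driven by noise. The display needs a plain label, a confirmed companion row and a like-for-like reference.

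**What to change.** Change the analysis only; the home alert and the site's handling of it stay as they are.

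1. Keep the present row in SAP 9.3, label it as any single unconfirmed home reading, and show the number of readings per child.
2. Add a confirmed row: the daily representative value of SAP 7.1.3 at or above the Table 9.d limit on at least 2 days of the same home week. The two-day threshold is a proposal with no source in the documents. Where a day has one reading, SAP 7.1.3 uses that reading as the daily value, so the row is less protected. With one reading a day throughout, putting p in place of q gives about 2% at SD 8 and 24% at SD 11.
3. Tabulate both rows by 7-day home week, including Week 0 (predose), so that each on-treatment week is set against a placebo run-in week of equal length. Give Week 6 its own window, since Table 7.h has none.

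The cost is SAP wording, a small programming change on data already in the CRF, and a few extra table rows. The confirmed row is less sensitive to an isolated spike, which the retained single-reading row covers.
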